8.9 Withdrawal Criteria

Women who become pregnant will be withdrawn from the study (see Section 4.5.1.2) and should refrain from taking ubrogepant. The patient should return to the clinic for Visit 15/ET procedures.

Patients who meet IP discontinuation criteria related to abnormal liver function tests (Section 9.5) and who are advised not to be re-challenged will be withdrawn from the study.

Patients who reply with “yes” to questions 4 or 5 in the suicidal ideation section or “yes” to any question in the suicidal behavior section of the C-SSRS should not receive any further

ubrogepant, must be withdrawn from the study, and should receive appropriate follow-up as in routine clinical practice, including the Safety Follow-up visit (Visit 16) if ubrogepant was taken.

A patient with a condition and/or a situation that, in the investigator's opinion, may put the patient at significant risk, may confound the study results, or may interfere significantly with the patient's participation in the study may be withdrawn from treatment.

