5.3 Methods for Masking/Blinding

Ubrogepant will be provided to patients in the ubrogepant arms. A modified double-dummy design will be used to maintain the study blind for the ubrogepant arms. Patients randomized

to the ubrogepant arms will be provided IP in identical blister cards to maintain the blinding, and instructed to take 2 tablets to treat their migraine attack regardless of the dose group to which they are assigned. The patients randomized to the usual-care arm will not be dispensed ubrogepant.

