5.5 Method for Assignment to Treatment Groups/Randomization

Prior to initiation of study treatment, each patient who provides informed consent will be assigned a patient number that will serve as the patient identification number on all study documents.

At the time of randomization (ie, Visit 2), eligible patients will be randomly assigned to 1 of 3 treatment arms in a 1:1:1 ratio to receive usual-care, ubrogepant 50 mg, or ubrogepant 100 mg or [REDACTED].

[REDACTED]

An automated interactive web response system (IWRS) will be used to manage the randomization and treatment assignment. Allergan Biostatistics (randomization programmer) will prepare the randomization codes.

Investigational product will be labeled with medication kit numbers. The IWRS will provide the site with the specific medication kit number(s) for each randomized patient in the ubrogepant arms at the time of randomization. Sites will dispense IP according to the IWRS instructions. Sites will receive the IWRS confirmation notifications for each transaction. All notifications will be maintained with the study source documents.

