6.2.7 Suicidality Assessment

The C-SSRS is a clinician-rated instrument that reports the severity of both suicidal ideation and behavior. Suicidal ideation is classified on a 5-item scale: Type 1 (wish to be dead), Type 2 (nonspecific active suicidal thoughts), Type 3 (active suicidal ideation with any methods [not plan] without intent to act), Type 4 (active suicidal ideation with some intent to act, without specific plan), and Type 5 (active suicidal ideation with specific plan and intent). The C-SSRS also captures information about the intensity of ideation, specifically the frequency, duration, controllability, deterrents, and reasons for the most severe types of ideation. Suicidal behavior is classified on a 5-item scale: Type 0 (no suicidal behavior), Type 1 (preparatory acts or behavior), Type 2 (aborted attempt), Type 3 (interrupted attempt), and Type 4 (actual attempt). More than 1 classification can be selected provided they represent separate episodes. For actual attempts only, the actual or potential lethality is classified for the initial, most lethal, and most recent attempts. The C-SSRS will be completed at all study visits. At all visits, the C-SSRS will be completed for ideation and behavior since the previous visit. The C-SSRS will be completed on the eTablet by the investigator or designee with current and valid training in administering the assessment. A patient should not be released from the study center until the results of C-SSRS are reviewed and it is confirmed that the patient is not considered to be at risk.

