7.1.2 Safety Population

The Safety population will be defined separately for the ubrogepant arms and the usual-care arm.

- Ubrogepant arms: All randomized patients who received ≥ 1 dose of treatment
- Usual-care arm: All randomized patients in the usual-care arm.

The purpose of the usual-care arm is to contextualize any safety findings that may occur in the ubrogepant treated patients over the course of 12 months. As such, data from all patients randomized to the usual-care arm, regardless of whether the patient used medication to treat migraine, will be included in the safety analyses.

[REDACTED]

[REDACTED]

[REDACTED]

[REDACTED]

[REDACTED]

[REDACTED]

[REDACTED]

[REDACTED]

[REDACTED]

[REDACTED]

[REDACTED]

- | [REDACTED]
- | [REDACTED]
- | [REDACTED]
- | [REDACTED]
- | [REDACTED]
- | [REDACTED]
- | [REDACTED]
- | [REDACTED]
- | [REDACTED]
- | [REDACTED]
- | [REDACTED]
- | [REDACTED]

[REDACTED]
[REDACTED]
[REDACTED]

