7.3.2.1 Adverse Events

AEs will be coded by system organ class and preferred term using the Medical Dictionary for Regulatory Activities.

An AE will be considered a treatment-emergent adverse event (TEAE) if it was present after the first dose of treatment in the lead-in study or was present before the date of the first dose of treatment in the lead-in study and increased in severity after the first dose of treatment in the lead-in study. If more than 1 AE was reported before the first dose of treatment of the lead-in study and coded to the same preferred term, the AE with the greatest severity will be used for comparison with the AEs occurring after the first dose of treatment of the lead-in study. An AE that occurs after Visit 16 for patients with Visit 16, or more than 30 days after the last visit or last treatment, whichever is later, for patients without Visit 16 will not be considered as a TEAE.

The number and percentage of patients reporting TEAEs after randomization in each treatment group will be tabulated by descending percentage in the highest dose group, by system organ class and preferred term, and further categorized by severity and causal relationship to the study treatment. If more than 1 AE is coded to the same patient, the patient will be counted only once for that preferred term using the greatest severity and strictest causality for the summarization by severity and causal relationship.

The incidence of common ($\geq 2\%$ of patients in any treatment group) TEAEs will be summarized by system organ class, preferred term, and treatment group.

The total number of TEAEs by severity and causal relationship to the study treatment will be summarized by treatment group.

A SAE that occurred between the date of the first dose of treatment in the lead-in study and Visit 16 for patients with Visit 16, or within 30 days after the last visit or last treatment, whichever is later, for patients without Visit 16, inclusive, will be considered an on-therapy SAE. The number and percentage of patients who have on-therapy SAEs after randomization will be summarized by preferred term and treatment group.

The number and percentage of patients who had AEs leading to premature discontinuation of the study treatment will be summarized by preferred term and treatment.

For all screened patients, separate tabular displays will be presented for patients who died, patients with SAEs, and patients with AEs leading to premature discontinuation.

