8.8 Early Discontinuation of Patients

A premature discontinuation will occur when a patient who signed the informed consent form (ICF) and was randomized ceases participation in the study, regardless of circumstances, before completion of the study. Patients can be prematurely discontinued from the study for 1 of the following reasons:

- AE
- Protocol violation
- Noncompliance with ubrogepant
- Withdrawal of consent (a clear reason must be documented)
- Lost to follow-up (every effort must be made to contact the patient; a certified/traceable letter must be sent)
- Lack of qualifying event (a qualifying migraine is not treated within 6 months)
- Pregnancy
- Other reasons

Patients may voluntarily withdraw from the study at any time. Notification of early patient discontinuation from the study and the reason for discontinuation will be made to Allergan and will be clearly documented on the appropriate eCRF. All randomized patients who prematurely discontinue from the study, regardless of cause, should be seen for a final assessment. A final assessment will be defined as completion of the evaluations scheduled for Visit 15/ ET. If the patient discontinues prematurely, the patient is expected to return for a Safety Follow-up visit 4 weeks after Visit 15/ET.

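### Section 8.9 ties Visit 16 after a C-SSRS withdrawal to having taken ubrogepant, while Section 8.8 expects that visit of every randomized patient who stops early

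*Protocol*

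**What the plan says.** Protocol Section 8.8 places a premature discontinuation at the point when "a patient who signed the informed consent form (ICF) and was randomized ceases participation in the study, regardless of circumstances", before the study is complete. For such patients it sets a final assessment (the Visit 15/ET evaluations) and then adds: "If the patient discontinues prematurely, the patient is expected to return for a Safety Follow-up visit 4 weeks after Visit 15/ET". It attaches no condition on arm or on drug intake.

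Protocol Section 8.9 deals with patients who answer yes to ideation question 4 or 5, or to any behavior question, on the C-SSRS. They get no more ubrogepant, must leave the study, and should have suitable routine-practice follow-up, "including the Safety Follow-up visit (Visit 16) if ubrogepant was taken". The paragraph does not mention arm, randomization status or Section 8.8.

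Three other provisions matter here. On usual care, Section 5.3 states: "The patients randomized to the usual-care arm will not be dispensed ubrogepant". Section 6.2.7 states: "The C-SSRS will be completed at all study visits". Suicidality during the Safety Follow-up period is summarized by treatment group in the Safety population (Protocol Section 7.3.2.6; SAP Section 5.1.1.4.7, Table 5-26).

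**The concern.** A randomized patient withdrawn under the C-SSRS rule is covered by both sections, and they describe Visit 16 differently. A site handling a suicidality withdrawal is likely to turn to the paragraph written for that event. Read literally, its condition cannot be met in the usual-care arm by anything that happens in this study, and it is not met by a ubrogepant-arm patient who never dosed.

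What is at stake is first the care of a patient at raised risk, who could miss the scheduled contact four weeks after exit. Second, the usual-care arm exists to put ubrogepant safety findings in context. If dosed patients return after a suicidality withdrawal and usual-care patients do not, follow-up is uneven by arm in the very patients for whom the assessment matters most.

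**Working it through.** The plan gives no figure to reproduce on this point. The check sets the two rules side by side.

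1. **Overlap.** Section 8.8 covers anyone randomized who stops early for any reason. A randomized patient who must be withdrawn under 8.9 meets that definition, so both sections apply.

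2. **Result by type of patient**, reading *taken* as taken in this study:

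| Patient with a qualifying C-SSRS response | Visit 16 under 8.8 | Visit 16 under 8.9, read literally |
|---|---|---|
| Ubrogepant arm, at least one dose | Expected | Called for |
| Ubrogepant arm, no dose | Expected | Not called for |
| Usual care | Expected | Not called for |
| Positive before randomization | Outside 8.8 | Only if ubrogepant was taken |

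 The last row exists because the C-SSRS is done at every visit, while assignment comes later: "At the time of randomization (ie, Visit 2), eligible patients will be randomly assigned to 1 of 3 treatment arms". The two sections differ in rows two and three.

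3. **What would be missed.** Visit 16 falls 4 weeks after Visit 15/ET. Since the C-SSRS is done at all study visits, Visit 16 carries the one scheduled C-SSRS after the exit visit.

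4. **Whether it reaches the analysis.** In the usual-care arm every randomized patient is in the Safety population, so a missed Visit 16 leaves that patient without a scheduled follow-up-phase C-SSRS in the by-arm summary. For the ubrogepant arms the Safety population is "All randomized patients who received ≥ 1 dose of treatment". Undosed patients there are outside it, so for them only care is affected.

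5. **Adverse event window.** Section 7.3.2.1 does not count as treatment-emergent an event occurring "more than 30 days after the last visit or last treatment, whichever is later, for patients without Visit 16". With Visit 16 the window closes about 4 × 7 = 28 days after Visit 15/ET. Without it, the window closes no earlier than 30 days after the last visit. The difference is 30 − 28 = 2 days in the longer direction, so the window is not shortened.

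6. **Intent, as context only.** The Amendment 1 summary (Section 12.4) explains the 8.8 change by saying that patients in every arm need to come back for Safety Follow-up. Both sides of the mismatch are current sections and do not depend on that log. It does suggest that the 8.9 condition is a leftover.

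**The case against.** The strongest answer is that 8.8 already settles the matter. It is explicit, covers all randomized patients whatever the cause, and states no exception. Section 8.9 lists Visit 16 as something included in follow-up and never says *only*. Nor does 8.9 try to name every exit visit: its pregnancy paragraph mentions just Visit 15/ET, and its liver paragraph names no visit, although Section 9.5 requires Visits 15 and 16 of patients who are not rechallenged. The qualifier also has a sensible use for patients who are C-SSRS-positive before randomization. Table 1 and the visit-procedure text cannot be seen and may remove any doubt.

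Most of this stands. A reader might infer that 8.9 bars Visit 16 for usual-care patients, or that the protocol contradicts itself outright. The text supports neither; 8.8 on its face still applies. What remains is that 8.9 is the more specific rule, that this paragraph alone in 8.9 puts a condition on Visit 16, and that it neither limits the condition to patients before randomization nor refers to 8.8.

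A reader might also infer a measurable bias in the usual-care follow-up percentage. The documents do not support a figure. They give no rate of C-SSRS withdrawals and no rate of recurrent ideation or behavior at Visit 16. SAP Table 5-2 allows a denominator other than the whole population, and the table specifications are in a separate document. A triggering response after randomization is itself a C-SSRS record, and Table 5-26 has its own treatment phase and a listing of all values, so the main signal is kept.

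**Conclusion.** The point holds as a minor misalignment between two current sections. A site following 8.9 literally could omit Visit 16 and its C-SSRS for a usual-care patient, or an undosed ubrogepant-arm patient, withdrawn for suicidality, even though 8.8 expects the visit. The number affected cannot be estimated from the documents, is likely very small and may be zero. The main effect is on patient follow-up: the suicidality summary is descriptive, and Visit 15/ET and routine clinical follow-up still apply.

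This rests on two assumptions. One is that *taken* means taken in this study; the text does not say whether lead-in doses count. If they do, the gap narrows to randomized patients who took no ubrogepant in either study. The other is that the unseen Table 1 and visit procedures do not already resolve it.

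**What to change.** In Section 8.9, replace the closing condition on Visit 16 with: *for all randomized patients, in any arm (see Section 8.8), and for any other patient who took ubrogepant*. The first part matches 8.8. The last part leaves patients who are C-SSRS-positive before randomization as they are now, including any who took ubrogepant in the lead-in study if those doses count. Check that Table 1 and the visit procedures say the same.

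The cost is one phrase in the protocol. It adds no visit for randomized patients beyond those 8.8 already expects, and no change to the SAP is needed.

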8.10 Study Termination

Allergan may stop the study (and/or the study site) for any reason with appropriate notification.

9. Adverse Events

AEs occurring during the study will be recorded on an AE eCRF. If AEs occur, the first concern will be the safety of the study participants.

9.1 Definitions

9.1.1 Adverse Event

An AE is any untoward medical occurrence in a patient or clinical investigation patient administered a pharmaceutical product and that does not necessarily have a causal relationship with this treatment. An AE can therefore be any unfavorable and unintended sign (including an abnormal laboratory finding), symptom, or disease temporally associated with the use of a medicinal (investigational) product, whether or not related to the medicinal (investigational) product. In addition, during the screening period, AEs will be assessed regardless of the administration of a pharmaceutical product.

Note: AEs must be collected once informed consent has been obtained, regardless of whether or not the patient has been administered study drug.

Progression of treatment indication including new or worsening of anticipated clinical signs or symptoms, which are collected as clinical efficacy variables and assessed as unequivocally associated with the disease progression and/or lack of efficacy, should NOT be reported as AEs unless the disease progression is greater than anticipated in the natural course of the disease.

AEs will be assessed, documented, and recorded in the eCRF throughout the study (ie, after informed consent has been obtained). At each visit, the investigator will begin by querying for AEs by asking each patient a general, non-directed question such as “How have you been feeling since the last visit?” Directed questioning and examination will then be done as appropriate. All reported AEs will be documented on the appropriate case report form.

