A Phase 2b clinical study was conducted, which compared 1, 10, 25, 50, and 100 mg doses of ubrogapant to placebo in the acute treatment of migraine. Overall, all the ubrogapant doses tested were well tolerated and the adverse event (AE) profile of all ubrogapant doses did not differ significantly from placebo. For the primary efficacy endpoint of pain freedom at 2 hours, ubrogapant doses of 1 and 10 mg did not differ from placebo, but doses of 25, 50, and 100 mg were better than placebo. For the primary efficacy endpoint of pain relief at 2 hours none of the ubrogapant doses differed from placebo, probably due to a high placebo response rate.

The absence of migraine-associated symptoms of photophobia, phonophobia, and nausea were assessed as key secondary endpoints. Ubrogapant doses of 50 and 100 mg were significantly better than placebo for absence of phonophobia and photophobia at 2 hours, whereas 25 mg did not differ from placebo. None of the ubrogapant doses differed from placebo for the endpoint of absence of nausea at 2 hours. Measures of sustained migraine headache relief (2 to 24 hours and 2 to 48 hours SPF and sustained pain relief) generally suggested that ubrogapant 50 mg and 100 mg were more effective than the 25 mg dose.

This trial is being conducted to evaluate the long-term safety and tolerability of ubrogepant for the acute treatment of migraine.

The purpose of including the usual-care arm will be to contextualize any safety findings that may occur over the course of a year in the ubrogepant arms. In open-label designs without a comparator arm, it can be difficult to interpret any safety findings that may arise in the experimental treatment arm. The proposed inclusion of the usual-care arm in this study is intended to address this limitation. Because of the stated purpose of the usual-care arm, efficacy data will not be collected from patients randomized to this arm.

2. Study Objectives and Clinical Hypotheses

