6.4 Summary of Methods of Data Collection

An IWRS will be used to randomize patients and manage ubrogepant inventory. Data for this study will be collected using eCRFs via an electronic data capture system. Source documents will be used at the sites and may include a patient's medical record, hospital charts, clinic charts, the investigator's patient study files, as well as the results of diagnostic tests, such as laboratory tests, ECGs, etc. Centralized vendors will be used for the analysis of all blood/urine samples and ECG assessments. Additional information on the collection and handling of samples is detailed in respective laboratory manuals.

Patients in the ubrogepant arms will use an eDiary to record details associated with their migraine attack, [REDACTED]

[REDACTED]. Patients in the usual-care arm will use the eDiary to record details associated with their migraine attack before it is treated with their usual medication.

The C-SSRS will be conducted as a clinical interview at each visit and recorded by a qualified site staff member via an eTablet.

7. Statistical Procedures

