7.1 Analysis Populations

7.1.1 Modified Intent-to-Treat Population

The Modified Intent-to-Treat (mITT) population will consist of all randomized patients who received at least 1 dose of IP (ubrogepant) and had at least 1 post-treatment efficacy

assessment in this study. The mITT population is only defined for the ubrogepant arms, as no efficacy measurements will be collected from patients in the usual-care arm.

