5.1.1.1 Common Conventions

5.1.1.1.1 Analysis Populations

The analysis populations will consist of participants as defined below:

Table 5-1 Analysis Populations

Population	Definition	Study Treatment
Screened	All screened participants who signed informed consent	—
Intent-to-Treat (ITT)	All randomized participants.	Randomized assignment
Modified Intent-to-Treat (mITT)	All randomized patients who received at least 1 dose of IP (ubrogapant) and had at least 1 posttreatment efficacy assessment in this study. The mITT population is only defined for the ubrogapant arms, as no posttreatment efficacy measurements will be collected from patients in the usual-care arm.	Randomized assignment
Safety	The Safety population is defined separately below for the ubrogapant arms and the usual-care arm. Ubrogapant arms: All randomized patients who received ≥ 1 dose of treatment. Usual care arm: All randomized patients in the usual-care arm. The purpose of the usual care arm is to contextualize any safety findings that may occur in the ubrogapant treated patients over the course of 12 months. As such, data from all patients randomized to the usual care arm, regardless of whether the patient used medication to treat migraine, will be included in the safety analyses.	Actual received

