TEAEs	Summary by 
 • SOC and PT for all participants and by subgroup analyses: 
 ○ by Sex ○ by Age Group <40 vs \geq40 ○ by Age Group <65 vs \geq65 ○ by Race White vs All other races ○ by cardiovascular risk category ○ by renal function class • SOC and PT for concomitant medication classes used by at least 10% of participants in at least one treatment group • SOC, PT, and AE onset time intervals 
 ○ <3 months ○ \geq3 and <6 months ○ \geq6 and <9 months ○ \geq9 and <12 months ○ \geq12 months • SOC, PT, and average number of migraine attacks treated with study treatment per month 
 ○ \geq2 ○ \geq4 ○ \geq6 	From randomization date to Visit 16 for participants with Visit 16, or within 30 days after last visit or last treatment, whichever is later, for participants without Visit 16	Categorical descriptives

Parameter	Description	Timing	Methodology
	
 ○ ≥8 • SOC, PT, and severity • SOC, PT, and causal relationship to the study treatment • Type (Mild, Moderate, Severe, related, not related) • SOC and PT for TEAEs occurring in ≥ 2% of participants in any ubrogapant treated dose group (and greater than placebo) 		
Common TEAEs	Summary by PT 
 • Includes TEAEs occurring in ≥ 2% of participants in any treatment group 	From randomization date to Visit 16 for participants with Visit 16, or within 30 days after last visit or last treatment, whichever is later, for participants without Visit 16	Categorical descriptives
On-therapy SAEs ¹	Overall summary and by PT	From randomization date to Visit 16 for participants with Visit 16, or within 30 days after last visit or last treatment, whichever is later, for participants without Visit 16	Categorical descriptives
On-therapy fatal SAEs	Participants who report On-therapy fatal SAEs will have their fatal SAEs and all AEs listed	From randomization date to Visit 16 for participants with Visit 16, or within 30 days after last visit or last treatment, whichever is later, for participants without Visit 16	Categorical descriptives
AEs leading to discontinuation ²	Overall summary and by PT	From randomization date to Visit 16 for participants with Visit 16, or within 30 days after last visit or last treatment, whichever is later, for participants without Visit 16 ²	Categorical descriptives

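### The rule keeping migraine symptoms out of the AE data depends on efficacy-variable status, which usual care lacks after treatment; read literally, it could raise migraine-related AE counts in that arm only.

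*Protocol*

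**What the plan says.** Protocol Section 9.1.1 sets the exemption. It concerns new or worsening signs and symptoms of the treated condition and covers those "which are collected as clinical efficacy variables and assessed as unequivocally associated with the disease progression and/or lack of efficacy, should NOT be reported". The two conditions are joint, and no arm is named. The section then makes one exception, under which a symptom stays reportable: "unless the disease progression is greater than anticipated in the natural course of the disease".

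Protocol Section 1 states that "efficacy data will not be collected from patients randomized to this arm". Section 7.1.1 defines the mITT population for the ubrogepant arms only, "as no efficacy measurements will be collected from patients in the usual-care arm". The SAP is narrower: Table 5-1 (Section 5.1.1.1.1) restricts the population "as no posttreatment efficacy measurements will be collected from patients in the usual-care arm".

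Usual care does record some migraine data. Protocol Section 6.4 says: "Patients in the usual-care arm will use the eDiary to record details associated with their migraine attack before it is treated". Section 8.5 gives the eDiary instruction to all patients.

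Sections 1 and 7.1.2 give the purpose of the usual-care arm as context for the ubrogepant safety findings. Only the choice between 50 mg and 100 mg is blinded (Sections 3 and 5.3).

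**The concern.** The filter on AE reporting depends on a property, efficacy-variable status, that the protocol denies to one arm. A site following the text word for word could exempt persisting nausea or returning headache in a ubrogepant patient and have no basis for exempting the same symptom in a usual-care patient. Asking the same open question in every arm does not prevent this, because the difference would arise when the answers are filtered. The investigator doing the filtering knows whether the patient is on ubrogepant or usual care.

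Safety is the primary outcome, and usual care is the only non-ubrogepant arm. Extra disease symptoms counted there would favour ubrogepant. The terms affected would include nausea, where a drug effect and a disease symptom are hard to tell apart.

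**Working it through.** The plan states no figure to reproduce: the readable text gives no expected AE rate. The check is a comparison of texts, followed by an illustration of scale.

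**1. Which symptoms are efficacy variables?** The protocol's list is redacted. SAP Section 5.1.1.1.4 still shows headache severity, migraine-associated symptoms, and recurrence questions at 24 and 48 hours. Protocol Section 1 lists the associated symptoms as photophobia, phonophobia and nausea.

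**2. Can the first condition of 9.1.1 be met?**

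| Symptom | Ubrogepant arms | Usual care, literal reading | Usual care, trial-wide reading |
|---|---|---|---|
| Recorded in the eDiary before treatment | Yes | Arguable: recorded, but the protocol denies any efficacy data | Yes |
| Persisting, worsening or returning after treatment | Yes, where collected | No | Yes |

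The trial-wide reading takes the condition to mean any type of symptom that the trial uses for efficacy. The arms separate only under the literal reading, and clearly only for post-treatment symptoms.

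**3. Illustration of scale.** Inputs: n = 400 per arm (Protocol Section 4.1). Assumed: a true term rate p, equal in all arms, and a share q of usual-care patients who have migraine symptoms entered as AEs because of the rule, independent of p. The apparent usual-care rate is 1 − (1 − p)(1 − q), so the spurious difference is q(1 − p).

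For p = 5% and q = 2%: 1 − 0.95 × 0.98 = 6.9%, a gap of 1.9 points, or 7.6 extra patients of 400.

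| q | Gap, p = 2% | Gap, p = 5% | Gap, p = 60% (any TEAE) |
|---|---|---|---|
| 0 (trial-wide reading) | 0 | 0 | 0 |
| 1% | 0.98 | 0.95 | 0.40 |
| 2% | 1.96 | 1.90 | 0.80 |
| 5% | 4.90 | 4.75 | 2.00 |
| 10% | 9.80 | 9.50 | 4.00 |

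Gaps are in percentage points, usual care higher. At p = 5%, the ratio of ubrogepant to usual care is 0.840, 0.725, 0.513 and 0.345 for q = 1%, 2%, 5% and 10%. The overall TEAE rate moves little; single overlapping terms move more.

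**4. Would such a gap stand out?** No interval for AE differences is planned in the readable text. For scale, the Wald 95% half-width for 3% v 6% is 1.96 × √[(0.03 × 0.97 + 0.06 × 0.94)/400] = 2.87 points, against a gap of 3.0. For 3% v 5% it is 1.96 × √[(0.03 × 0.97 + 0.05 × 0.95)/400] = 2.71 points, against a gap of 2.0. The answer depends entirely on the assumed excess.

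**5. Effect on a filtered table.** SAP Table 5-20 includes a TEAE table limited to terms at 2% or more in a ubrogepant dose group and above placebo. The trial has no placebo arm. Suppose that usual care fills that role, and consider one dose arm with a term truly at 4% against 2% in usual care. The term is kept if its count k is at least 8 (2% of 400) and exceeds the usual-care count. The probability is the sum over k ≥ 8 of P(k; 400, 0.04) × P(usual-care count ≤ k − 1). It is 0.94 at q = 0, 0.755 at 1%, 0.475 at 2% and 0.029 at 5%.

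**The case against.** The strongest reply is that 9.1.1 names no arm and can be read as describing types of symptom. On that reading every arm is treated alike and there is no bias. This stands as a possible reading. The documents neither state it nor show what sites were told.

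Other points limit the scope:

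- Usual-care patients record pre-treatment attack details, and the SAP denies only post-treatment measurements. This stands, and it narrows the gap to post-treatment symptoms.
- A symptom must also be judged unequivocally due to the disease or to lack of efficacy. Nausea that might be a drug effect stays reportable on ubrogepant. A reader might infer that all nausea during attacks is dropped from the ubrogepant arms; the text does not say that.
- A strictly literal reading does not give full exemption on ubrogepant either. Attacks not treated with ubrogepant under the conditions of Section 5.6.1 may lack efficacy data too. This would reduce the contrast.
- The treatment-emergent definition in SAP Table 5-19 may remove some habitual symptoms. The documents do not show how many.
- TEAEs are tabulated by preferred term, so an excess of headache or nausea in usual care would be visible. Its cause would not be.

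These points reduce the certainty and likely size of the problem. None supplies an arm-neutral rule.

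**Conclusion.** The wording of 9.1.1 permits AE ascertainment that differs by arm. If sites apply it literally, migraine-overlapping terms may be over-recorded in usual care relative to ubrogepant, and ubrogepant would look relatively safer on those terms. The size is unknown: zero under the trial-wide reading and, for a term at 5%, about 1 to 9.5 points over an assumed excess of 1% to 10%. Laboratory, ECG and C-SSRS data do not pass through this rule.

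A reader might infer that usual-care AE rates are in fact inflated, or that the artefact would show as a clear difference. The documents support neither. They show an ambiguous rule, no rates and a descriptive safety analysis, and the gap in step 4 falls on either side of its half-width according to the excess assumed. Nor can the 2% cut-off for common TEAEs ("Includes TEAEs occurring in ≥ 2% of participants in any treatment group") be used to show harm from a 3% true rate, because 3% already exceeds it.

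The point is still worth acting on. The comparison is open-label, the arm concerned exists to put the safety findings in context, and the literal error would run in favour of the test drug.

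**What to change.** Reword Protocol Section 9.1.1, or issue equivalent site guidance, so that the exemption refers to signs and symptoms of the indication and applies identically in all three arms, whether or not they are efficacy variables in that arm. Keep the two existing safeguards: the requirement for an unequivocal association, and the exception for progression beyond the natural course.

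In the SAP, add one supplementary TEAE table that removes a prespecified list of migraine-symptom preferred terms from every arm. Show it beside the unrestricted TEAE table. It needs no new data and remains useful if collection has already finished.

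The cost is one sentence and one table. Slightly fewer AEs may be recorded in usual care. Read alone, the restricted table could hide a drug effect on nausea, so it must be read with the full table and must not replace it.
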